## **10. QUALITY CONTROL AND QUALITY ASSURANCE**

During study conduct, Pfizer or its agent will conduct periodic monitoring visits to ensure that the protocol and GCPs are being followed. The monitors may review source documents to confirm that the data recorded on CRFs is accurate. The investigator and institution will allow Pfizer monitors or its agents and appropriate regulatory authorities direct access to source documents to perform this verification.

The study site may be subject to review by the institutional review board (IRB)/independent ethics committee (IEC), and/or to quality assurance audits performed by Pfizer, or companies working with or on behalf of Pfizer, and/or to inspection by appropriate regulatory authorities.

It is important that the investigator(s) and their relevant personnel are available during the monitoring visits and possible audits or inspections and that sufficient time is devoted to the process.

## **11. DATA HANDLING AND RECORD KEEPING**

### **11.1. Case Report Forms / Electronic Data Record**

As used in this protocol, the term case report form (CRF) should be understood to refer to either a paper form or an electronic data record or both, depending on the data collection method used in this study.

A CRF is required and should be completed for each included subject. The completed original CRFs are the sole property of Pfizer and should not be made available in any form to third parties, except for authorized representatives of Pfizer or appropriate regulatory authorities, without written permission from Pfizer.

The investigator has ultimate responsibility for the collection and reporting of all clinical, safety and laboratory data entered on the CRFs and any other data collection forms (source documents) and ensuring that they are accurate, authentic / original, attributable, complete, consistent, legible, timely (contemporaneous), enduring and available when required. The CRFs must be signed by the investigator or by an authorized staff member to attest that the data contained on the CRFs is true. Any corrections to entries made in the CRFs, source documents must be dated, initialed and explained (if necessary) and should not obscure the original entry.

In most cases, the source documents are the hospital's or the physician's subject chart. In these cases data collected on the CRFs must match the data in those charts.

In some cases, the CRF, or part of the CRF, may also serve as source documents. In these cases, a document should be available at the investigator's site as well as at Pfizer and clearly identify those data that will be recorded in the CRF, and for which the CRF will stand as the source document.

### **11.2. Record Retention**

To enable evaluations and/or audits from regulatory authorities or Pfizer, the investigator agrees to keep records, including the identity of all participating subjects (sufficient information to link records, eg, CRFs and hospital records), all original signed informed consent forms, copies of all CRFs, safety reporting forms, source documents, and detailed records of treatment disposition, and adequate documentation of relevant correspondence (eg, letters, meeting minutes, telephone calls reports). The records should be retained by the investigator according to International Conference on Harmonization (ICH), local regulations, or as specified in the [Clinical Study Agreement \(CSA\)](#), whichever is longer.

If the investigator becomes unable for any reason to continue to retain study records for the required period (eg, retirement, relocation), Pfizer should be prospectively notified. The study records must be transferred to a designee acceptable to Pfizer, such as another investigator, another institution, or to an independent third party arranged by Pfizer. Investigator records must be kept for a minimum of 15 years after completion or discontinuation of the study or for longer if required by applicable local regulations.

The investigator must obtain Pfizer's written permission before disposing of any records, even if retention requirements have been met.

## **12. ETHICS**

### **12.1. Institutional Review Board (IRB)/Independent Ethics Committee (IEC)**

It is the responsibility of the investigator to have prospective approval of the study protocol, protocol amendments, informed consent forms, and other relevant documents, eg, recruitment advertisements, if applicable, from the IRB/IEC. All correspondence with the IRB/IEC should be retained in the Investigator File. Copies of IRB/IEC approvals should be forwarded to Pfizer.

The only circumstance in which an amendment may be initiated prior to IRB/IEC approval is where the change is necessary to eliminate apparent immediate hazards to the subjects. In that event, the investigator must notify the IRB/IEC and Pfizer in writing immediately after the implementation.

### **12.2. Ethical Conduct of the Study**

The study will be conducted in accordance with legal and regulatory requirements, as well as the general principles set forth in the [International Ethical Guidelines for Biomedical Research Involving Human Subjects \(Council for International Organizations of Medical Sciences 2002\)](#), [Guidelines for Good Clinical Practice \(International Conference on Harmonization 1996\)](#), and the [Declaration of Helsinki \(World Medical Association, 1996 and 2008\)](#).

In addition, the study will be conducted in accordance with the protocol, the [International Conference on Harmonisation guideline on Good Clinical Practice](#), and applicable local regulatory requirements and laws.

### **12.3. Subject Information and Consent**

All parties will ensure protection of subject personal data and will not include subject names on any sponsor forms, reports, publications, or in any other disclosures, except where required by laws.

Subject names, address, birth date and other identifiable data will be replaced by an alpha-numerical code consisting of a numbering system provided by Pfizer in order to de-identify the trial subject. In case of data transfer, Pfizer will maintain high standards of confidentiality and protection of subject personal data.

The informed consent form must be in compliance with ICH GCP, local regulatory requirements, and legal requirements.

The informed consent form used in this study, and any changes made during the course of the study, must be prospectively approved by both the IRB/IEC and Pfizer before use.

The investigator must ensure that each study subject, or his/her legal representative, are fully informed about the nature and objectives of the study and possible risks associated with participation.

The investigator, or a person designated by the investigator, will obtain written informed consent from each subject or the subject's legal representative, and subject assent when appropriate, before any study-specific activity is performed. The investigator will retain the original of each subject's or the subject's legal representative signed consent document. Informed consent should be obtained from the parent(s) or legal representative before assent is sought.

An assent from the subject will be obtained in addition to the consent when appropriate, and when the potential subject is capable of providing assent. The determination of appropriateness and capacity is made by the investigator and/or the relevant IRB or IEC, and should take into account the age, maturity, and psychological state of the potential subject. Assent is not required if the investigator and/or the IRB/IEC determine that the capability of the child or adolescent subject is so limited that they cannot provide assent.

When applicable, full informed consent from “emancipated minors” is both necessary and sufficient, rather than assent plus the consent of a legally acceptable representative or representatives.

If a minor becomes of age following assent and enrolment in the study, a consent must be signed once the subject turns legal age, based on local requirements.

#### **12.4. Subject Recruitment**

Advertisements approved by ethics committees and investigator databases may be used as recruitment procedures. Other methods, for example, increasing awareness of the study through patient associations, may be used as appropriate, and subject to approval by ethics committees.

#### **12.5. Reporting of Safety Issues and Serious Breaches of the Protocol or ICH GCP**

In the event of any prohibition or restriction imposed (ie, clinical hold) by an applicable Competent Authority in any area of the World, or if the investigator is aware of any new information which might influence the evaluation of the benefits and risks of the investigational product, Pfizer should be informed immediately.

In addition, the investigator will inform Pfizer immediately of any urgent safety measures taken by the investigator to protect the study subjects against any immediate hazard, and of any serious breaches of this protocol or of ICH GCP that the investigator becomes aware of.

### **13. DEFINITION OF END OF TRIAL**

#### **13.1. End of Trial in a Member State**

End of Trial in a Member State of the European Union is defined as the time at which it is deemed that sufficient subjects have been recruited and completed the study as stated in the regulatory application (ie, [Clinical Trial Application \(CTA\)](#)) and ethics application in the Member State. Poor recruitment (recruiting less than the anticipated number in the [CTA](#)) by a Member State is not a reason for premature termination but is considered a normal conclusion to the study in that Member State.

#### **13.2. End of Trial in all Participating Countries**

End of Trial in all participating countries is defined as Last Subject Last Visit.

### **14. SPONSOR DISCONTINUATION CRITERIA**

Premature termination of this study may occur because of a regulatory authority decision, change in opinion of the IRB/IEC, drug safety problems, or at the discretion of Pfizer. In addition, Pfizer retains the right to discontinue development of fesoterodine at any time.

If a study is prematurely terminated or discontinued, Pfizer will promptly notify the investigator. After notification, the investigator must contact all participating subjects and the hospital pharmacy (if applicable) within a time period set by Pfizer. As directed by Pfizer, all study materials must be collected and all [CRFs](#) completed to the greatest extent possible.

### **15. PUBLICATION OF STUDY RESULTS**

#### **15.1. Communication of results by Pfizer:**

Pfizer fulfills its commitment to publicly disclose clinical trial results through posting the results of this study on [www.clinicaltrials.gov](http://www.clinicaltrials.gov) ([ClinicalTrials.gov](#)). Pfizer registers study protocols and posts Basic Results on [ClinicalTrials.gov](#) for Pfizer-sponsored interventional studies in human subjects that evaluate the safety and/or efficacy of a Pfizer product

The results are posted in a tabular format called Basic Results.

For studies involving a Pfizer product, the timing of the posting depends on whether the Pfizer product is approved for marketing in any country at the time the study is completed:

- For studies involving products applicable under the US Food and Drug Administration Amendments Act of 2007 (FDAAA), ie, FDA-approved products, Pfizer posts results within one year of the primary completion date (PCD). For studies involving products approved in any country, but not FDA approved, Pfizer posts results one year from last subject, last visit (LSLV).

- For studies involving products that are not yet approved in any country, Pfizer posts the results of already-completed studies within 30 days of US regulatory approval, or one year after the first ex-US regulatory approval of the product (if only submitted for approval ex-US);
- For studies involving products whose drug development is discontinued before approval, Pfizer posts the results within one year of discontinuation of the program (if there are no plans for outlicensing or within two years if outlicensing plans have not completed).

Primary Completion Date is defined as the date that the final subject was examined or received an intervention for the purposes of final collection of data for the primary outcome, whether the clinical trial concluded according to the pre-specified protocol or was terminated.

## **15.2. Publications by Investigators**

Pfizer has no objection to publication by Investigator of any information collected or generated by Investigator, whether or not the results are favorable to the Investigational Drug. However, to ensure against inadvertent disclosure of Confidential Information or unprotected Inventions, Investigator will provide Pfizer an opportunity to review any proposed publication or other type of disclosure before it is submitted or otherwise disclosed.

Investigator will provide manuscripts, abstracts, or the full text of any other intended disclosure (poster presentation, invited speaker or guest lecturer presentation, etc.) to Pfizer at least 30 days before they are submitted for publication or otherwise disclosed. If any patent action is required to protect intellectual property rights, Investigator agrees to delay the disclosure for a period not to exceed an additional 60 days.

Investigator will, on request, remove any previously undisclosed Confidential Information (other than the study results themselves) before disclosure.

If the study is part of a multi-centre study, Investigator agrees that the first publication is to be a joint publication covering all centers. However, if a joint manuscript has not been submitted for publication within 12 months of completion or termination of the study at all participating sites, Investigator is free to publish separately, subject to the other requirements of this Section.

For all publications relating to the study, Institution will comply with recognized ethical standards concerning publications and authorship, including Section II “[Ethical Considerations in the Conduct and Reporting of Research](#)” of the [Uniform Requirements for Manuscripts Submitted to Biomedical Journals](#), <http://www.icmje.org/index.html#authorship>, established by the [International Committee of Medical Journal Editors](#).

Publication of study results is also provided for in the [Clinical Study Agreement](#) between Pfizer and the institution. In this section entitled Publications by Investigators, the defined terms shall have the meanings given to them in the [Clinical Study Agreement](#).

### **Appendix 1. Examples of CYP3A4 Inducers and Potent CYP3A4 Inhibitors**

Potent CYP3A4 inhibitors within 3 weeks prior to Visit 2 (baseline), or the expectation to start such a treatment during the trial, as well as medications capable of inducing CYP3A4 enzyme metabolism are prohibited.

The following table provides examples of such medications. The lists are provided for your reference only and are not intended to be all-inclusive. Please consult a member of the study team for further clarification if necessary.

CYP3A4 Inducers	Potent CYP3A4 Inhibitors
efavirenz nevirapine barbiturates carbamazepine glucocorticoids modafinil oxcarbazepine phenobarbital phenytoin pioglitazone rifabutin rifampin St. John's wort Troglitazone	indinavir nelfinavir ritonavir clarithromycin itraconazole ketoconazole nefazodone saquinavir telithromycin

## Appendix 2. Total Volume of Trial-Related Blood Loss

BLOOD TEST		FESOTERODINE 2, 4 or 8 mg				OXYBUTYNIN	
		Volume of whole blood				Volume of whole blood	
Test panel	Test	Visit 1 Screening Week 0	Visit 3 Week 4	Visit 5 Week 12	Visit 7 Week 24	Visit 1 Screening	Visit 5 Week 12
Hematology	Hemoglobin Hematocrit RBC count Platelet count WBC count with differential of total neutrophils, eosinophils, monocytes, basophils, lymphocytes	2 ml	N/A	2 mL	2 mL	2 ml	2 ml
Chemistry	GOT (AST) GPT (ALT) GGT Total and direct bilirubin Alkaline phosphatase Lactate dehydrogenase (LDH) Creatine phosphokinase (CPK) Blood urea nitrogen (BUN) Creatinine Uric acid Total protein Albumin Sodium Potassium Chloride Bicarbonate Phosphorus Corrected calcium Glucose (non-fasting)  Serum pregnancy test (in females of childbearing potential only) a	3.5 ml	N/A	3.5 mL	3.5 mL	3.5 ml	3.5 ml
Pharmacokinetic	5-HMT	N/A	6 mL	N/A	N/A	N/A	N/A
Pharmacogenomic	CYP2D6	N/A	2 mL	N/A	N/A	N/A	2 mL
Total blood volume	Total volume per visit	5.5 ml	8 mL	5.5 ml b	5.5 mL	5.5 ml	7.5 ml
	Total volume over study	24.5 mL b				13 mL	

N/A - not applicable. Additional blood samples may be taken as needed to follow-up on significant findings, or as clinically indicated. The total volume does not include discarded blood from predraws used to remove fluid from flushed catheters at Visit 3. The discarded volume is not anticipated to exceed 1.65 ml based on 3 draws using winged infusion (butterfly) set with a priming volume of 0.55 ml (23G, ¾ inch, 12 inch tubing).

a Serum pregnancy test at Screening (Visit 1) only (urine testing at subsequent visits)

b For fesoterodine treatment groups, if no PG sample is required (due to prior genotyping), total blood volume at Visit 3 = 6 ml, total blood volume over the study = 22.5 mL.

	Guidelinesa	A0221047 blood loss volume (volume including discarded bloodd)
Maximum total volume at a single time	20 ml b	13.5 ml (16.25 ml)
Maximum total volume in a 4 week period	60 ml c	13.5 ml (16.25 ml)
Maximum possible total volume in a 4 week period (assuming subject withdraws prior to Visit 5, and within 4 weeks of Screening at Visit 1)	60 ml	19 ml (22.3 ml)

a As per *Ethical Considerations for Clinical Trials on Medicinal Products Conducted with the Paediatric Population (Section 13.2)* [http://ec.europa.eu/health/files/eudralex/vol-10/ethical\\_considerations\\_en.pdf](http://ec.europa.eu/health/files/eudralex/vol-10/ethical_considerations_en.pdf). Accessed 24 Nov 2010: Per individual, the trial-related blood loss (including any losses in the manoeuvre) should not exceed 3 % of the total blood volume during a period of four weeks and should not exceed 1% at any single time. Subjects weighing less than 17 kg will be very unusual, especially for this population, and the breach of maximum guidelines volume is minor if it does happen, and it should be possible to stay within guideline limits by a very minor reduction in draw volume that does not affect ability to analyse.

b 1 % is 0.8 ml/kg = 0.8 ml x 25 kg = 20 ml at single time assuming minimum body weight of 25 kg and total volume of blood of 80 ml/kg body weight; for a 17 kg subject the volume is 13.6 mL,

c 3% is 2.4 ml/kg = 2.4 ml x 25 kg = 60 ml in a 4 week period assuming minimum body weight of 25 kg and total volume of blood of 80 ml/kg body weight; for a 17 kg subject the volume is 40.8 mL

d Assuming that predraws (to remove fluid from flushed catheters) are performed between each sample taken and based on a winged infusion (butterfly) set with a priming volume of 0.55 ml (23G, 3/4 inch, 12 inch tubing).

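### Protocol Appendix 2: the declared single-time blood maximum with discard (16.25 mL) exceeds its own 1% limit below 20.3 kg, not 17 kg as footnote a implies

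*Protocol*

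**What the plan says.** Protocol Appendix 2 sets the trial's blood loss against a paediatric ethics guideline. Footnote a reports a four-week limit, "the trial-related blood loss (including any losses in the manoeuvre) should not exceed 3 % of the total blood volume", and a limit for one occasion, "should not exceed 1% at any single time". Footnote b takes blood volume as 80 mL/kg, so the single-time limit is 0.8 mL/kg. The table's guideline column prints 20 mL, the value at 25 kg, which footnote b calls the minimum body weight. Footnote b also notes that "for a 17 kg subject the volume is 13.6 mL".

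The trial's own single-time cell reads "13.5 ml (16.25 ml", the bracketed figure counting discarded blood. Footnote d gives the basis for the discard: "Assuming that predraws (to remove fluid from flushed catheters) are performed between each sample taken", at 0.55 mL each. A separate note, about Visit 3, is less generous: "The discarded volume is not anticipated to exceed 1.65 ml based on 3 draws".

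Footnote a then concedes a breach for light children: "Subjects weighing less than 17 kg will be very unusual, especially for this population, and the breach of maximum guidelines volume is minor". It adds that the limit can be kept by a "very minor reduction in draw volume that does not affect ability to analyse".

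Four other places bear on this:

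- Section 1.2 defines Cohort 2 as 25.0 kg and below, with no lower bound.
- Section 6.12 and Schedule of Activities note i ask for PK samples from fesoterodine subjects who withdraw before Visit 3 (Week 4), plus the Visit 5 assessments where possible.
- Note j places genotyping of fesoterodine subjects at Visit 3. At Visit 5 or early withdrawal it asks only subjects coming off oxybutynin.
- Section 7.4 states the genotyping requirement in general terms and gives no early-termination timing.

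**The concern.** Footnote a counts discarded blood against the limit, so the figure to test is 16.25 mL and not 13.5 mL. The appendix does not show how 17 kg was chosen, but 17 kg does not fit 16.25 mL. The guideline cell hides this: 16.25 mL looks comfortable beside 20 mL, yet that margin belongs to the heaviest child Cohort 2 can enrol. Lighter children are foreseen, since SAP Section 6.4 plans a Cohort 2 subgroup at or below 20 kg.

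The appendix is the protocol's safety justification for drawing blood from small children. A site or ethics committee reading it cannot tell which volume the 17 kg belongs to, or how large a reduction a light child would need.

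**Working it through.** **Inputs.** Limit 0.8 mL/kg at one time and 2.4 mL/kg over four weeks (Appendix 2, footnotes b and c). PK 3 x 2 = 6 mL and genotype 2 mL (Section 6.5). Safety bloods 5.5 mL (Section 6.7). Discard 0.55 mL per predraw (footnote d). All draws at one visit count as a single time, as the table itself does.

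**Reproducing the plan's figures.**

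- Single-time maximum: 6 + 2 + 5.5 = 13.5 mL.
- With discard: 13.5 + 5 x 0.55 = 16.25 mL. The five predraws are three PK, one genotype and one for the safety bloods.
- Four-week worst case: 13.5 + 5.5 (screening) = 19 mL, and 19 + 6 x 0.55 = 22.3 mL.
- Limit at 17 kg: 0.8 x 17 = 13.6 mL.

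All agree with the appendix, so the declared maximum includes a genotype sample.

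**Weight at which each draw reaches 1%** (total loss / 0.8), and excess over 13.6 mL at 17 kg:

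| Draw at one visit | Drawn (mL) | Predraws | Total (mL) | Threshold (kg) | Excess at 17 kg |
|---|---|---|---|---|---|
| Declared maximum, discard ignored | 13.5 | 0 | 13.5 | 16.9 | none |
| Declared maximum, with discard | 13.5 | 5 | 16.25 | 20.3 | 2.65 mL (19.5%) |
| Early termination, no genotype | 11.5 | 3 | 13.15 | 16.4 | none |
| Same | 11.5 | 4 | 13.7 | 17.1 | 0.1 mL (0.7%) |
| Same | 11.5 | 5 | 14.25 | 17.8 | 0.65 mL (4.8%) |
| Early termination, no genotype or third PK | 9.5 | 3 | 11.15 | 13.9 | none |
| Scheduled Visit 3 | 8 | 3 | 9.65 | 12.1 | none |
| Scheduled Visit 3, genotype with own predraw | 8 | 4 | 10.2 | 12.8 | none |

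At 20 kg the limit is 16.0 mL, so the declared maximum is over by 0.25 mL (1.6%).

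**Predraw count.** The protocol prints no discard total for the draw without a genotype sample. Removing the genotype predraw from the five above leaves four. The Visit 3 note allows only three for three PK samples plus a genotype sample, which suggests that tubes can share a predraw. Hence the range of three to five.

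**Four weeks.** 22.3/2.4 = 9.3 kg, so that limit is not in question.

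**The case against.** The strongest reply is that 16.25 mL is a stacked worst case. It needs a fesoterodine withdrawal before Visit 3, the optional third PK sample (Section 7.3.1), Visit 5 bloods that are requested only where possible, a genotype sample that neither Section 6.12 nor note j requests at that visit, and a separate predraw for every draw. For what the withdrawal text does ask for, 17 kg is about right, and with three predraws it is slightly cautious. An over-inclusive maximum in a safety table errs in the safe direction. Some relief is already written in: footnote a points to a smaller draw, and Section 6.7 lets Visit 5 run over two days, although Section 6.12 does not expressly extend that to withdrawal visits.

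Most of this stands, and it limits the point to a minor one. It does not reconcile the table with its footnote. The table counts a genotype sample even in its withdrawal row, and Section 7.4 leaves the timing open, so a site could follow either reading.

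A reader might infer that Cohort 2 children under 20.3 kg are due to be overdrawn, or that a routine visit breaches the limit. The documents do not support that. Scheduled Visit 3 is within 1% down to about 12 to 13 kg. Nor do the documents give a Cohort 2 weight distribution, so the number of children affected cannot be estimated.

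**Conclusion.** The inconsistency is real and follows from the appendix's own numbers. For the maximum it declares, the threshold is 20.3 kg, and keeping a 17 kg child within the limit would mean cutting total loss by 2.65/16.25 = 16%, which is not a very small reduction. The 20.3 kg figure needs no assumption beyond the appendix's own volumes and discard. The thresholds of 16.4 to 17.8 kg for the draw without a genotype sample do rest on an assumed three to five predraws, and 13.7 mL is a derived figure that is not printed in the protocol.

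The practical reach is one unscheduled visit in light Cohort 2 children who stop fesoterodine before Visit 3. Cohort 1 is not touched, since above 25 kg the limit exceeds 20 mL. No endpoint, analysis, power or eligibility rule depends on it. Severity is minor.

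**What to change.** For Cohort 2, state the single-time limit as 0.8 mL/kg including discard, in place of a single 20 mL figure, and cap any single-visit draw at it. At fesoterodine early termination, confirm that no genotype sample is taken. If the cap would still be exceeded, omit the optional third PK sample (about 11.15 mL, threshold 13.9 kg) or split the draws over two days.

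Then make table and footnote agree by restating the single-time maximum as 11.5 mL (about 13.7 mL with discard, assuming four predraws), with a threshold of about 17 kg. Recalculate the four-week rows that carry the same 13.5 mL. Only if the sponsor does want a genotype sample at that visit should 16.25 mL stay, and then 20.3 kg should be stated as its threshold.

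The cost is a few table cells, one footnote and one instruction. The downside is a few lost PK samples, or an extra visit day, in light children who withdraw early.
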